#### *Pupillary Diameter*

Summary statistics of the observed values (averages by occasion) and change from baseline for the parameters listed in Section 8.1 (INIT, END, ACV, MCV, ADV, T75) will be reported. In addition, to assess the treatment difference between CST-103/CST-107 and placebo, a mixed model with baseline, treatment sequence, period, timepoint (i.e., Day 1: 4 hrs post-dose, Day 7: 4 hrs post-dose, Day 14: 4 hrs post-dose), disease type, and treatment as fixed effects, and a random subject effect, will be analyzed, with the LS mean, LS mean difference, and p-value for the LS mean difference will be reported for each pupillometry parameter noted above.

#### *Geriatric Depression Scale (GDS)*

The GDS is a 30-item self-administered yes/no question test constructed for brief screening of depression in elderly persons. Total scores are the summation of scored responses (responses indicating worsening depression equate to 1, and responses indicating lessening depression equate to 0) from each question. Scores greater than 9 are considered suspect for depression. The GDS will be administered on Day 1 (Baseline), Day 7, and Day 14 of each treatment period. Summary statistics of total scores and change from baseline will be presented. A mixed model with change from baseline as the outcome, baseline as a covariate, fixed effects for treatment sequence, period, timepoint (i.e., Day 7, Day 14), disease type, and treatment, and subject as a random effect will be analyzed. LS mean, LS mean difference and its associated p-value will be reported.

All GDS data, included responses to individual questions, will be listed.

#### *Hospital Anxiety and Depression Scale (HADS)*

HADS is a 14-item questionnaire with subscales for anxiety and depression. Subjects are given 14 questions in multiple-choice format, seven about depressive symptoms and seven about anxiety symptoms and are asked to give a score from 0 to 3 where 0 is the least depressed/anxiety option and 3 the most. Depression and Anxiety sub-scores are recorded in the electronic database and are calculated as the sum of responses to the 7 questions within the

Sponsor: CuraSen Therapeutics, Inc.  
Protocol Number: CST103/CST107-CLIN-011  
Version and Date: █████ v1.0 / 24May2022

category. HADS will be administered on Day 1 (Baseline) and Day 14 of each treatment period. Summary statistics of sub-scores and changes from baseline will be reported. A mixed model to assess the treatment effect, including fixed effects baseline, treatment sequence, period, timepoint (i.e., Day 14), disease type, and treatment, and random subject effect will be analyzed, and LS means, LS mean differences, and associated p-value will be presented.

HADS data will be listed.

### 8.3. Exploratory Endpoints and Analyses

The FAS will be used for all exploratory endpoint analyses unless stated otherwise.

#### Cohort A and Cohort B

##### *Inflammatory Biomarkers*

Inflammatory biomarkers include C-reactive protein and cytokine levels and will be collected at Day 1 (Baseline) and Day 14 of each treatment period. Descriptive statistics of observed values and change from baseline will be presented for both biomarkers. Inflammatory biomarker data will also be listed.

##### *Neurodegenerative Biomarkers*

Neurodegenerative biomarkers including neurofilament light chain, total and phosphorylated tau protein, and amyloid- $\beta$  (A $\beta$ ) peptides will also be collected at Day 1 (Baseline) and Day 14 of each treatment period. Similar to inflammatory biomarker data, descriptive statistics of the neurodegenerative biomarkers and change from baseline to Day 14 will be summarized. All neurodegenerative biomarker data will be listed.

##### *Sustained Attention to Response Task (SART, Cohort B AUS Subjects from Site 502 only)*

SART is a computer-based go/no-go task that requires participants to withhold behavioral response to a single, infrequent target presented among a background of frequent non-targets. The subject is asked to respond to the non-target and inhibit their response to the target. Parameters collected include error rate and reaction time. The SART will be administered prior to dosing on Day 1 (Baseline) and 3 hours post-dose on Days 1 and 14 of each treatment period. SART data will be reported in by-subject listings.

##### *Freezing of Gait Questionnaire (FOG-Q, RBD+PD, DLB, and PDD Subjects Only)*

The FOG-Q assesses Freezing of Gait (FOG) and consists of six items borrowed from the Gait and Falls Questionnaire. Each question ranges from 0 to 4, with higher scores indicating worsening gait. FOG-Q will be administered on Day 1 (Baseline) and Day 14 of each treatment

Sponsor: CuraSen Therapeutics, Inc.  
Protocol Number: CST103/CST107-CLIN-011  
Version and Date: [REDACTED] v1.0 / 24May2022

period. Summary statistics of responses to each of the six question and change from baseline will be reported. FOG-Q data will additionally be listed.

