2. STUDY OBJECTIVES AND ENDPOINTS

2.1. Study Objectives

The primary objective of this study is to identify a CNS signal in one of the planned pharmacodynamic measurements after multiple oral doses of CST-103 in the presence of CST-107 in four populations of subjects with Neurodegenerative Disorders (NDD):

Cohort A

1. Parkinson's Disease (PD) with REM Sleep Behavior Disorder (RBD) and Depressive Symptoms
2. Mild Cognitive Impairment (MCI) with Depressive Symptoms

Cohort B

3. Dementia with Lewy Bodies (DLB) with Cognitive Fluctuations
4. Parkinson's Disease Dementia (PDD) with Cognitive Fluctuations

These pharmacodynamic assessments will compare the effect of CST-103 co-administered with CST-107 with that of placebo on the following:

Cohort A

- Emotional Facial Processing

Cohort B

- Cognitive fluctuations

The secondary objectives for all subjects include the comparison of the effect of CST-103 co-administered with CST-107 with that of placebo on the following:

1. Cognition
2. Movement and time spent sitting, standing and sleeping
3. Sleep
4. Pupillary reactivity
5. Mood Assessment
6. Safety and tolerability of CST-103 co-administered with CST-107
7. The pharmacokinetic (PK) profiles of CST-103 and CST-107

The exploratory objectives are to characterize the effect of CST-103 co-administered with CST-107 on the following:

1. To characterize the effect of CST-103 co-administered with CST-107 on inflammatory biomarkers in blood, such as C-reactive protein and cytokine levels may be measured.
2. To characterize the effect of CST-103 co-administered with CST-107 on neurodegenerative biomarkers in the blood such as neurofilament light chain, total and phosphorylated tau protein, and amyloid- β ($A\beta$) peptides may also be evaluated.
3. To characterize the effect of CST-103 co-administered with CST-107 on performance of a sustained attention task in Cohort B subjects.
4. To characterize the effect of CST-103 co-administered with CST-107 on Freezing of Gait (FOG) (for subjects with RBD+PD, PDD and DLB).
5. To characterize the locus coeruleus volume and contrast ratio (this is an optional objective based on imaging capabilities).

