5.3.6.9. **Sustained Attention to Response Task (SART) -- DLB and PDD Subjects at Select Sites Only**

The Sustained Attention to Response Task (SART) is a computer-based go/no-go task that requires participants to withhold behavioral response to a single, infrequent target (often the digit 3) presented amongst a background of frequent non-targets. There is evidence supporting the role of the SART as a measure of working memory, sustained attention, and impulse/inhibitory control. In this task, the participant is asked to respond (e.g., button press) to the non-target and to inhibit their response to the target. To perform well, individuals must remain sufficiently attentive to their responses, such that, at the appearance of a target, they can override the dominant pre-potent motor response and substitute the directly antagonistic response (i.e., withhold button press) ([Phillips 2020](#)).

5.3.6.10. **Freezing of Gait Questionnaire — RBD+PD, DLB and PDD Subjects Only**

Freezing of Gait (FOG) is one of the most frequent and disabling symptoms in Parkinson’s disease (PD) affecting about half of all patients, especially in the advanced stages of disease. The Freezing of Gait Questionnaire (FOG-Q) is considered a valid and reliable tool for the assessment of FOG severity. The FOG-Q consists of six items borrowed from the Gait and Falls Questionnaire ([Giladi 2000](#)).

5.3.6.11. **Verbal Fluency Test**

Verbal fluency tests are widely used for assessing executive function and require the generation of words from initial letters (phonological verbal fluency) or belonging to a specific category (semantic fluency), under a time constraint.

The specific versions of verbal fluency used in this study are the ‘ALPHABET’ and ‘CATEGORY’ tests from the Brief And Simple Index of Cognition (BASIC) (Harrison 2000).

For the ALPHABET task, subjects are given 1 minute to say aloud as many words they can think of that begin with the letter F, avoiding repetitions or the same words with different endings. The total score is the number of correct words generated.

For the CATEGORY task, subjects are given 1 minute to say aloud as many animals they can think of, avoiding repetitions. The total score is the number of animals generated.

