### 5. DATA ANALYSIS CONSIDERATIONS

All analyses will be conducted based on SAS 9.4 or higher.

All data in the database will be presented in by-subject data listings.

Unless otherwise stated, all listings will be sorted by cohort, disease type, treatment sequence, subject number, and assessment date (and time, if available).

Unless stated otherwise, continuous data will be summarized by cohort, disease type, treatment sequence and overall based on n, mean, median, standard deviation (SD), minimum value, and maximum value.

Unless stated otherwise, categorical data will be summarized by cohort, disease type, treatment sequence and overall using n and percentage based on the number of nonmissing values.

- The number of missing values will be presented as a separate category with no percentage, but only if one or more subjects are missing data.
- Counts of zero will be presented without percentages.

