## 8. ENDPOINT ANALYSES

All inferential analyses are exploratory in nature given that this study was not powered based on any statistical assumptions. All efficacy data will be presented by cohort, disease type, and treatment assigned at the time of data collection.

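### Freezing of gait is reported only as six item tables: SAP 8.3 prespecifies no FOG-Q total score and no within-subject treatment difference with a confidence interval

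*SAP*

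**What the plan says.** - **Objective.** Protocol 2.1 lists as exploratory: "To characterize the effect of CST-103 co-administered with CST-107 on Freezing of Gait (FOG) (for subjects with RBD+PD, PDD and DLB". Protocol 2.4 names the FOG-Q as the matching endpoint.
- **Instrument.** Protocol 5.3.6.10 describes the FOG-Q as one six-item questionnaire that "is considered a valid and reliable tool for the assessment of FOG severity".
- **Collection.** The Schedule of Events places it on Day 1 and Day 14 of both treatment periods, for RBD+PD, DLB and PDD subjects. It is not collected at Screening.
- **Analysis.** SAP 8.3 gives the item scale ("Each question ranges from 0 to 4, with higher scores indicating worsening gait") and then the whole plan: "Summary statistics of responses to each of the six question and change from baseline will be reported"; "FOG-Q data will additionally be listed". It contains no total, missing-item rule, model, treatment difference or interval.
- **Layout.** SAP section 8 opens with: "All efficacy data will be presented by cohort, disease type, and treatment assigned at the time of data collection". The general default in SAP section 5 differs: "Unless stated otherwise, continuous data will be summarized by cohort, disease type, treatment sequence and overall".
- **Protocol analysis sections.** Protocol 8.9 (exploratory endpoints) does not name the FOG-Q. Protocol 8.10 groups it with the screening scales, which are only to be listed.

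**The concern.** The protocol treats the FOG-Q as one measure of freezing severity, while the SAP splits it into six ordinal items and never puts them together. Nor does it estimate how much a subject's score differs between active and placebo. That within-subject difference is what the crossover is there to deliver: both documents justify the design by its extra precision over a parallel trial.

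At stake is whether the study report can give one prespecified estimate of the effect on freezing, with its uncertainty, or only six pairs of columns. Item responses are listed, so a total could be built later, but choosing it after unblinding would make it post hoc. SAP 4.1 expects most subjects to be RBD+PD, so much of the trial will supply these data.

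**Working it through.** **1. How the FOG-Q compares with the other measures in the SAP**

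| Measure | Tier | Score defined | Treatment difference estimated |
|---|---|---|---|
| ESS | secondary | total of 8 items | yes, mixed model |
| GDS | secondary | total of 30 items | yes, mixed model |
| HADS | secondary | two sub-scores | yes, mixed model |
| FOG-Q | exploratory | none | no |
| Inflammatory and neurodegenerative biomarkers | exploratory | not applicable | no |
| SART, neuromelanin MRI | exploratory | not applicable | no, listed only |

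The missing model is common to the whole exploratory tier. Among these four questionnaires, the missing score is peculiar to the FOG-Q.

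**2. Which layout applies.** The section 5 default (by sequence) yields where something else is stated, and the opening of section 8 (by treatment) states something else. By treatment is therefore the better reading for 8.3. It is not followed throughout section 8, however: the CANTAB text in 8.2 returns to treatment sequence. One sentence in 8.3 would settle it.

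**3. What the unused pairing could be worth.** The plan gives no figure for the FOG-Q. Its only power statement (protocol 8.1, SAP 4.3) covers primary and cognition-related secondary endpoints: 80% power for 0.79 SD with 20 subjects and for 0.54 SD with 40, at a between-period correlation ρ of 0.3 and a two-sided 5% level. It reproduces:

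- SD of the within-subject difference = SD × √(2(1 − ρ)) = SD × √1.4 = 1.183 SD.
- N = 20: noncentrality (0.79/1.183) × √20 = 2.99; power 80.6% on 18 df.
- N = 40: noncentrality (0.54/1.183) × √40 = 2.89; power 80.3% on 38 df.

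Borrowing that set-up for illustration only:

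- A reader who combines the two treatment columns as if they were independent groups must use √2 = 1.414 SD. The ratio to the paired value is 1.414/1.183 = 1.20, so the standard error is about 20% larger than needed at ρ = 0.3. At ρ = 0 there is no loss.
- Approximate 95% CI half-width for the paired difference: 2.10 × 1.183/√20 = 0.56 SD at N = 20, and 2.02 × 1.183/√40 = 0.38 SD at N = 40.

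The documents give neither the number of FOG-Q subjects nor the FOG-Q correlation between periods. N = 20 to 40 is an assumed range, and ρ = 0.3 is the plan's value for other endpoints.

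**4. Total against single item.** Six items scored 0-4 give a sum from 0 to 6 × 4 = 24; the documents define no total. Suppose each item's treatment difference has the same SD, any two correlate r, and m of the six items carry the same effect. The standardised effect on the sum, relative to one responding item, is then m/√(6(1 + 5r)).

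| r (assumed) | m = 6 | m = 3 | m at which sum and item are equal |
|---|---|---|---|
| 0.4 | 6/√18 = 1.41 | 3/√18 = 0.71 | √18 = 4.2 |
| 0.6 | 6/√24 = 1.22 | 3/√24 = 0.61 | √24 = 4.9 |

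The sum gains if all six items respond and loses if only half do. At these correlations at least five must respond for it to come out ahead. The documents give no r and no item effects, so neither the sign nor the size of the gain can be fixed.

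**The case against.** The strongest case for leaving the plan alone has four parts.

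- **Comparison by treatment is already there.** A reader might infer from 8.3 that no treatment comparison is planned. The documents do not support that: the opening of section 8 puts active and placebo side by side for each item. What is missing is an estimated difference.
- **The objective is modest.** A reader might also infer that the objective cannot be answered. It asks only for a characterisation, is exploratory, and sits in a study declared descriptive with no formal hypothesis testing. Item tables by treatment plus listings meet it at a basic level.
- **The tier differs.** ESS, GDS and HADS are secondary, and protocol 8.8 plans treatment comparisons for that tier. No exploratory endpoint in SAP 8.3 gets a model, and SAP 8.3 already goes beyond protocol 8.10. This stands as a reason for low priority. It explains the missing model but not the missing total.
- **The benefit is uncertain.** Protocol 5.3.6.10 says freezing affects about half of Parkinson's patients, especially in advanced disease. Entry for FOG-Q subjects is limited to Modified Hoehn and Yahr stages 1 to 3, with no freezing criterion. Many scores near zero are plausible, and a total does not cure a floor. This stands too.

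Nor can a multiplicity benefit be claimed: no item-level tests are planned, so a single score removes none.

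**Conclusion.** The point holds in a limited form. SAP 8.3 leaves the FOG-Q without a prespecified total and without a within-subject active-minus-placebo estimate and interval. The crossover information is therefore unused, and the exploratory objective rests on six descriptive item tables. A sum with a model-based difference would let the trial size the effect.

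It is a low-severity improvement and invalidates nothing. The increases of 41% and 22% in standardised effect for the total (r = 0.4 and 0.6) need equal effects on all six items and correlations found nowhere in the documents, so they should not be quoted as the size of the problem. The 20% standard-error figure and the half-widths of 0.56 to 0.38 SD likewise rest on a correlation stated for other endpoints and an assumed N.

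**What to change.** In SAP 8.3:

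1. Define the FOG-Q total as the sum of the six 0-4 items (0-24), with a rule for missing items.
2. State that FOG-Q tables are by treatment.
3. Fit one exploratory mixed model on the FAS: Day 14 change in the total as outcome; period baseline as covariate; treatment sequence, period, disease type and treatment as fixed effects; subject as random. The HADS text should not be copied as it stands, since it names no dependent variable and carries a timepoint term with a single level. Day 14 is the only post-baseline FOG-Q visit, so no timepoint term is needed.
4. Report the LS mean difference with its 95% CI, labelled exploratory.
5. Keep the item summaries, which matter if only some items respond.
6. Reconcile with protocol 8.10, which lists the FOG-Q as a screening scale although it is collected on Days 1 and 14.

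The cost is one derived score and one extra exploratory model, with no new data or visits. The downside is that the total may be less sensitive than single items if effects are concentrated in a few of them or scores sit near zero.

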#### *Neuromelanin MRI Scan*

The neuromelanin-sensitive MRI sequence is optional depending on the imaging facility's capabilities, and can be performed at Screening. If not performed at Screening, it may be performed at the Follow-up visit or at any other convenient time during the study. Neuromelanin will be measured to evaluate its suitability as a biomarker of locus coeruleus integrity.

MRI data will be listed.

## 9. PHARMACOKINETICS

Details regarding PK sampling, including scheduled timepoint and actual date and time of blood draws will be listed. Additional analyses of PK data will be summarized in a separate analysis plan.

## 10. SAFETY

All safety analysis reporting will be based on the Safety Set. All safety summaries except for laboratory summaries will be presented by cohort, disease type, and treatment taken at time of data collection. Lab summaries will be presented by cohort, disease type, and treatment sequence.

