8.5. Statistical Methods

Statistical analyses will be performed using SAS 9.3 or higher. Continuous data will display number of subjects, means, standard deviations, median, minimum, and maximum. Categorical data will display frequency counts and percentages. As this study is descriptive in nature, no formal hypothesis testing will be performed. Unless specified otherwise, confidence intervals will be displayed at the two-sided 95% confidence level.

Summaries of disposition and baseline data will be summarized by cohort (A or B), disease criteria within cohort (RBD+PD or MCI for Cohort A, and PDD or DLB for Cohort B), treatment sequence and overall. Summaries of safety, pharmacodynamics, and PK will be presented by disease criteria, treatment (CST103/CST107 versus placebo) and overall. A limited subset of summaries may be presented by treatment sequence and/or period and overall.

For analysis purposes, Baseline will be defined as either the pre-dose measurement taken within each of the study periods, or as the last measurement before the first dose received. This will be detailed in the SAP for each parameter. All data will be listed.

Any changes in the planned analysis will be described and documented in the SAP and/or clinical study report.

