8.8.4. Analysis of Safety

Safety endpoints will be summarized by disease criteria, treatment and overall using the Safety Set. Additional summaries may be performed by treatment sequence and/or period. A limited set of endpoints may also be summarized using other analysis populations.

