8.8.8. Clinical Laboratory Results, Vital Signs, and ECGs

Absolute values and changes from baseline will be summarized by cohort, disease criteria, treatment and overall. In addition, clinical laboratory results and ECG shift tables may be generated.

All results will be listed. Laboratory values outside of normal ranges and clinically significant ECG abnormalities will be flagged.

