### 2.1. Changes from the Protocol

While two separate protocols govern the trial in Australia/New Zealand and the United Kingdom/European Union, all analyses will be performed cumulatively among subjects across all regions, except for BioStamp and SART analyses which are only collected on subjects from Australia and New Zealand.

Additionally, the protocol states that approximately 20 subjects will be enrolled in Cohort A with RBD+PD or MCI and approximately 20 subjects will be enrolled in Cohort B with PDD or DLB. Due to the difficulty in recruiting patients with DLB and PDD the majority of the subjects recruited will be in Cohort A and the majority of these are RBD+PD subjects. Cohort B data will be captured in listings and summarized in the demographics, disposition, secondary endpoint analyses, and exploratory analyses tables.

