### 6.5. Multiple Assessments and Visit Windows

Nominal visits (e.g. those identified by the study CRF) will be the basis of summarization and statistical analysis; no visit date windowing will be conducted. Unscheduled data may be included in summaries of specific abnormalities any time post-baseline and subject data listings.

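### SAP 10.1, read literally, leaves first-dosing-day events out of the TEAE counts, against SAP Appendix 1; as a lesser point, SAP 10 tabulates laboratory data by sequence, not treatment

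*SAP*

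**What the plan says.** **TEAE rule.** Three places define treatment emergence.

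- SAP 10.1 requires the onset to follow the date of first dose, up to study completion.
- SAP Appendix 1 has a row for fully known start dates. It flags an event whose start date equals or is later than the study drug start date.
- Protocol 8.8.5 counts events on or after the first dose.

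SAP 6.4 sends the reader to Appendix 1 when adverse event dates are missing.

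**Laboratory layout.** SAP 10 presents all safety summaries by the treatment being taken at data collection, except laboratory summaries, for which: "Lab summaries will be presented by cohort, disease type, and treatment sequence". SAP 10.2 adds summaries at each visit and shift tables. It offers box plots by treatment group for potassium and glucose, as an option.

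Protocol 8.8.8, covering laboratory results, vital signs and ECGs, says: "Absolute values and changes from baseline will be summarized by cohort, disease criteria, treatment and overall". Protocol 8.8.4 says: "Safety endpoints will be summarized by disease criteria, treatment and overall using the Safety Set". It then adds: "Additional summaries may be performed by treatment sequence and/or period". Protocol 8.5 also provides: "A limited subset of summaries may be presented by treatment sequence and/or period and overall", and: "Any changes in the planned analysis will be described and documented in the SAP and/or clinical study report". SAP 2.1, the section for changes from the protocol, does not mention the laboratory layout.

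**The concern.** Two TEAE rules in one SAP can give two TEAE counts from the same data, and the difference falls on the first day of exposure. Drug effects are plausible on that day: protocol 1.4.2.1 reports mild hypokalemia and hyperglycemia that resolved within hours of a single 160 µg dose of CST-103 in healthy subjects. That dose is higher than the planned one and was given in a different population, so it shows only that first-day events are possible.

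In a two-period crossover, every sequence contains both treatments, so a table with sequence columns does not show the treatment contrast directly. Safety and tolerability against placebo is a secondary objective. Protocol 1.5 names lower potassium and higher glucose among the effects that CST-107 is included to attenuate. Mean changes and range shifts that are not clinically significant appear only in the laboratory displays.

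**Working it through.** **1. TEAE boundary.** Let *d* be onset date minus date of first dose, with first dose meaning the first of the study.

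| *d* (days) | SAP 10.1, literal (*d* > 0) | SAP Appendix 1 (*d* ≥ 0) |
|---|---|---|
| −1 | no | no |
| 0 | **no** | **yes** |
| +1 | yes | yes |

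The rules differ on one date, Day 1 of Period 1. Day 1 of Period 2 comes after the first dose and counts under both. The disputed day is 1 of 14 dosing days in Period 1 (7.1%) and 1 of 28 overall (3.6%).

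Inputs are about 40 subjects and 1:1 allocation to two sequences (SAP 4.2 and 4.3), so 40 / 2 = 20 per sequence.

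- Active-first: the first active day is Day 1 of Period 1. Literal 10.1 omits it for 20 subjects.
- Placebo-first: the first active day is Day 1 of Period 2. It is counted for 20 subjects.
- The first active day is therefore counted for 20 / 40 = 50% under literal 10.1, and for 40 / 40 under Appendix 1 and protocol 8.8.5.
- The first placebo day mirrors this, with the sequences exchanged.

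Only tables restricted to TEAEs are affected. The full listing holds every event.

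Confining Appendix 1 to incomplete dates does not remove the problem. An event with start and stop dates both missing would be assumed treatment-emergent, while one dated exactly to the first dosing day would not.

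Appendix 1 compares dates only, so it also counts a Day 1 event that began before the dose. Such events can be recorded, because collection starts before dosing (protocol 8.8.5).

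**2. What sequence columns show.** For an additive treatment effect τ, pooling over periods gives (τ + 0)/2 in one sequence and (0 + τ)/2 in the other, a difference of 0. The contrast appears only when sequence is crossed with period visit. SAP 6.5 makes this possible: "Nominal visits (e.g. those identified by the study CRF) will be the basis of summarization and statistical analysis".

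**3. Cell sizes.** Assume *n* subjects in a disease type, balanced 1:1, with no dropout. Day 14 values fall in 2 sequences × 2 periods = 4 cells of *n*/2. By treatment they form 2 columns of *n*/2 + *n*/2 = *n*.

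SAP 2.1 expects that "the majority of the subjects recruited will be in Cohort A and the majority of these are RBD+PD subjects". Taking 40 in total, a majority is at least 21 in Cohort A, and a majority of 21 is at least 11 with RBD+PD. The number stays below 40, since a majority is not all and SAP 2.1 also plans Cohort B summaries.

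| RBD+PD *n* | Cell size | One subject as % of a cell | One subject as % of a treatment column |
|---|---|---|---|
| 11 | 5 or 6 | 1/5 = 20% or 1/6 = 16.7% | 1/11 = 9.1% |
| 20 | 10 | 1/10 = 10% | 1/20 = 5% |

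Counts, means and SDs can be recombined from the cells by hand. Medians cannot, but they can be recalculated from the listings.

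**4. Timing of laboratory samples.** The protocol's Schedule of Events asks for an 8-hour fast before safety labs, and protocol 7.2 has study drug taken after the first meal of the day. Together these imply that Day 14 samples precede that day's dose, although no clock time is stated.

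**The case against.** On the TEAE rule, the wording of 10.1 is probably loose drafting. Appendix 1 is the algorithm for treatment emergence, it agrees with protocol 8.8.5, and SAP 6.2 gives the dosing day a positive study day. That is a fair reading, and it makes the correction small. It does not make 10.1 and Appendix 1 agree.

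On the layout, the case against is stronger. Protocol 8.5 allows some sequence summaries and lets changes be documented in the SAP. SAP 10 states its exception openly, and nothing requires it to be repeated in SAP 2.1. The study is descriptive, with no formal testing. All of this stands. What remains is that SAP 10 gives no reason, and that a display which protocol 8.8.4 treats as additional has taken the place of the one by treatment.

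A reader might infer more than the documents support:

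- *That the overall column is dropped as well.* The default in SAP 5 is sequence and overall, and SAP 10 does not clearly remove it. Only the treatment grouping is firmly missing.
- *That acute potassium or glucose effects would be hidden.* The implied pre-dose sampling means that this point concerns Day 14 changes and shifts, not acute post-dose effects. Protocol 5.5 also expects hypokalemia to be unlikely with co-administration.
- *That laboratory abnormalities would escape the by-treatment tables.* Protocol 6.1.1 and 6.1.2 make clinically significant values adverse events, and those are tabulated by treatment. Protocol 6.2 adds a condition of symptoms or a change in concomitant therapy. These sections differ and need reconciling, so the narrower rule cannot be taken as settled.

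**Conclusion.** The TEAE conflict is firm. It lies inside the SAP, so it does not depend on the protocol version. Taken literally, 10.1 leaves out one day per subject, an active day for about half and a placebo day for the other half, assuming about 40 subjects at 1:1. The number of events affected cannot be derived from the documents. The omission is balanced between treatments in subject-days, so the documents do not support a claim that it favours one of them.

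The laboratory layout is a lesser point, held with less confidence. SAP 2 cites protocol versions 6.0 and 7.0. The supplied protocol's schedule has rows, such as APOE4 genotyping, that are absent from the SAP's copy, so it may be a different version. The inference that treatment information is lost is not supported: treatment follows from sequence and period visit, and every result is listed. The shortfall is that no planned laboratory table compares active with placebo directly, and the only by-treatment laboratory display is optional. Shift tables appear to inherit the sequence layout. For them the by-treatment expectation rests on protocol 8.8.4, because 8.8.8 makes them optional and gives them no grouping of their own.

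Both should be corrected before database lock.

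**What to change.** - **SAP 10.1:** define a TEAE as an event with onset on or after the date of first dose, the same rule as Appendix 1. If onset time is collected, use it in both places to exclude Day 1 events that began before the dose. Protocol 6.1.2 lists only the date of onset. If time is not collected, the date-only rule stands and 10.1 should say so.
- **SAP 10 and 10.2:** remove the laboratory exception. Present laboratory values, changes from baseline and shift tables by cohort, disease type, treatment at time of collection and overall, with sequence or period as a supplement. If the sequence layout is intended, give the reason in SAP 10 or 2.1.

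The cost is a few wording edits in SAP 10, 10.1 and, if onset time is used, Appendix 1, plus re-specified laboratory table columns. No new data are needed.
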